Surgical service lines will include orthopedic total joint, orthopedic spine, gynecology/oncology, thoracic, general, hernia, colorectal, open vascular, plastic, and open urological procedures. These lines will be randomized 1:1 to either the bundle of activities or usual care. The unit of randomization is the service line. The perioperative environment (the patient, the patient to follow, and all providers caring for the patient and the patient to follow) for the randomized service line (treatment or usual care) will be involved in surveillance. This means that all patients, all providers caring for those patients (changes day by day), and care environments (equipment and stopcock sets) will be involved in surveillance. Surveillance from treatment and control groups will yield *S. aureus* transmission events that will be processed to guide proactive improvements in the treatment bundle.

Treatment group (bundle) inclusion/exclusion criteria:

Inclusion criteria: Patients seen at UIHC who are scheduled to undergo surgery from providers in one of the service lines above, documentation of informed, written consent, >18 years of age, procedure requiring general/regional anesthesia.

Exclusion criteria: Lack of documented informed, written consent, patients <18 years of age, procedures outside of the surgical service lines listed above, not requiring general/regional anesthesia, patients not seen in the UIHC clinics, and an allergy to iodine/shellfish or chlorhexidine.

Usual care group (existing practice at UIHC) inclusion/exclusion criteria:

Inclusion criteria: Patients seen at UIHC who are scheduled to undergo surgery from providers in one of the service lines above, documentation of informed, written consent, >18 years of age, procedure requiring general/regional anesthesia.

Exclusion criteria: Lack of documented informed, written consent, patients <18 years of age, procedures outside of the surgical service lines listed above, not requiring general/regional anesthesia, patients not seen at UIHC, and an allergy to iodine/shellfish or chlorhexidine.

VI.14

Provide an estimate of the total number of subjects that would be eligible for inclusion in each of your study populations (include your control population if applicable)

We anticipate that >80% of all patients undergoing surgery in the surgical service lines above will be eligible for the study.

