We will be attempting to capture all patients that meet inclusion criteria which could include patients seen and consented in the clinic, seen and consented on the hospital floor, intensive care units (inpatient surgery), or pre-anesthesia testing (PAT). Any patient meeting inclusion criteria that the surgeon obtains surgical consent for could be captured. Poster reminders will be placed in the clinics, on the ward, and PAT. The study consent forms will be attached to the surgical consent forms. Surgical providers obtaining surgical consent will obtain study consent when possible. This will otherwise be executed via our research team via pager. Preoperative kit orders will be completed by surgical providers or physician study team members when needed. The signed and held order will populate a list in EPIC for the PI ([name]) that will be filtered by type of surgery, surgeon, and date of surgery within 10 days. It will include the patient medical record number, address/phone number, and an icon indicating the POC signed and held order. [name] will work the list to send ordered kits to patients. [name] will enter a new signed and held order for the kit and will associate the assigned kit number with the order, which will create a new ICON indicating ordered kit sent to patient. This will also update the Clarity report in EPIC with the kit number in addition to the other previously mentioned fields. The patient will receive the kit along with a reminder for why they received the kit (see attached in miscellaneous), use the kit (up to 3 reminders will be provided by [name] study team), and RDB will receive and process the kits. Patients will use a prepaid mailer to send the kits to RDB which will have the RDB address in the send and return fields so that patients are not revealing their identity to RDB (process okay per USPS). RDB will send returned kit numbers to [name] daily. [name] will complete the signed and held orders for patients in the Clarity report that returned kits for processing. The completed POC will generate another ICON indicating received and processed and will again update the Clarity report. The research assistants will work the list to select 2 patients with completed POC orders, treatment and control, for OR PathTrac Observation each day. The assistants will confirm 1st patient consent. Once confirmed, an OR PathTrac Kit will be ordered in EPIC which creates an ICON indicating consent confirmed, a consent confirmed box checked in the RDB microEMR will be placed (3 ways for tracking consents, the written document and two electronic confirmations), and the preoperative swab and OR PathTrac kit numbers entered into the microEMR along with baseline patient demographic information (OR room number and case number, surgery duration, date and time). Informed, written consent will be obtained from the second patient on the day of surgery (see attached consent for patient 2), an OR PathTrac Kit ordered, demographic information (see previous) entered into the microEMR, and surveillance completed. If the second patient does not provide consent for their samples, the pair will be excluded and recruitment continued to reach 1,000 pairs. Our prior experience and recent experience at the University of Iowa strongly suggests that patient refusal to provide written consent for intraoperative cultures will be a rare event. The assistant will then follow the 1st patient to the recovery area for sampling as previously described using the Ward Environment Surveillance (WES) kits. The WES kit number will be associated by the micro EMR to the other kit units. This

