- Use of any information available to the researchers or their colleagues because this person is a patient OR use of any information considered to be Protected Health Information (PHI) OR review of patient/clinic records - We will use the EPIC lists as previously described to send kits, track receipt, and guide surveillance. Email will be used to communicate with surgeons regarding subjects meeting inclusion criteria.
- Letter -

VII.D.2 *List the individual data elements you will need to access/use from the patient or clinic records to identify potential subjects for recruitment*

Age >18 (this will be differentiated by the order in EPIC where only patients age >18 have the order included in preoperative order sets)

Surgical clinic visit (involving orthopedic total joint, orthopedic spine, gynecology/oncology, cardiothoracic, general abdominal, colorectal, open vascular, general breast, and open urological procedures). Also documented allergies.

VII.D.3 *Describe why you could not practicably recruit subjects without access to and use of the information described above*

We cannot approach every patient in the clinic without this information.

VII.D.4 *Describe why you could not practicably obtain authorization from potential subjects to review their patient or clinic records for recruitment purposes.*

It is impractical for us to approach every patient in the clinic to get authorization to review their medical record.

VII.D.5 *Describe plans to protect the identifiers from improper use or disclosure*

The patients are protected by the HIPAA policy at the University of Iowa Hospitals and Clinics. PHI will be stored in EPIC. EPIC protects this data based on UIHC policy. Patient demographic factors entered into the RDB Bioinformatics will be de-identified, only associated to kit numbers. This information will be protected by 2-factor authentication and encrypted. A data safety plan signed by RDB and UIHC affiliates is in place.

Source documents (RDB kit inserts for reservoir collection, printed screen shots of the OR PathTrac microEMR, and patient demographic factor collection documents (see attached documents) will be kept in a binder that will be stored in a locked cabinet in the locked office of the PI.

Only research team members will have access to the EPIC lists of patient information linked to preoperative kit orders.

VII.D.6 *Describe plans to destroy identifiers at the earliest opportunity consistent with conduct of the research*

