 - Improved environmental cleaning: Environments (OR and ward) affected by high-risk S. aureus transmission events will be mapped by surveillance and addressed by automated reporting to the anesthesia workroom supervisor. This will trigger improvements in routine (standard cleaning using quaternary ammonium compound and micro cloth followed by a surface disinfection wipe) and terminal [improved routine technique followed by employment of robotic cleaning (Ultraviolet light)] cleaning.
- Fatigue mitigation: The team will use surveillance to continually monitor the impact and fatigue of the proposed interventions as conveyed by failure mode analysis of transmission dynamics involved clonal S. aureus transmission.

XI.2

Provide the rationale or power analysis to support the number of subjects proposed to complete this study.

Statistical Analysis: The unadjusted primary intention to treat analysis will compare the proportion of clonally-related S. aureus transmission events occurring in treatment vs. control perioperative (preoperative, intraoperative case pair, and postoperative) observational units across the 6 randomized service lines using the Chi squared test. We will assess for balance for variables known to be associated with intraoperative

transmission (case, duration > 2 hours, and discharge location). In the case of imbalance, we will use multivariate techniques to further explore the treatment effect using a generalized linear models approach.

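### The set and number of randomised service lines differ between VI.13, VII.D.2 and XI.2, so line membership, and the power that depends on it, is not fixed

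*Protocol*

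**What the plan says.** Protocol VI.13 names the lines as "orthopedic total joint, orthopedic spine, gynecology/oncology, thoracic, general, hernia, colorectal, open vascular, plastic, and open urological procedures", ten in all. It continues: "These lines will be randomized 1:1 to either the bundle of activities or usual care. The unit of randomization is the service line". Both groups' exclusion criteria rule out "procedures outside of the surgical service lines listed above".

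Protocol VII.D.2 asks which record data elements are needed "to identify potential subjects for recruitment". The answer gives age, allergies and surgical clinic visits in nine categories. The first three match VI.13; the other six are "cardiothoracic, general abdominal, colorectal, open vascular, general breast, and open urological procedures".

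Protocol XI.2 gives two counts. The primary analysis compares transmission "across the 6 randomized service lines"; the initial power analysis speaks of up to ten lines. The SAP names no lines and gives no count, but repeats its Poisson models clustered by surgeon or specialty.

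Three other sections depend on the list. VII.D.29 sends a treatment or control kit according to the patient's service line, and this sets the care given on the day of surgery. VII.D.26 plans no further check of the line, treating it as known. VI.14 divides expected patient numbers by the number of lines.

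**The concern.** The service line is the unit of randomisation. The list of lines therefore does three jobs: it fixes the number of clusters, it decides which patients are eligible, and it assigns each eligible patient to an arm. The protocol gives a ten-name list, a nine-name list that agrees with it on six names, and a count of six.

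Two things are at stake. First, allocation could be ambiguous for some patients. VI.13 randomises hernia and general as separate lines, so they may fall in opposite arms. If the recruitment list merges them under general abdominal, that category does not say which kit to send. Breast and cardiac cases have no named line in VI.13. Second, with between-line variation the power depends on the number of lines, and the stated 85% is not tied to a single number.

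**Working it through.** **Step 1. Compare the lists.**

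| VI.13 (randomised) | VII.D.2 (finding recruits) |
|---|---|
| orthopedic total joint | same |
| orthopedic spine | same |
| gynecology/oncology | same |
| colorectal | same |
| open vascular | same |
| open urological | same |
| thoracic | cardiothoracic |
| general | general abdominal |
| hernia | not named |
| plastic | not named |
| not named | general breast |

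That is ten names against nine, with six exact matches. Cardiothoracic is also a case type in the pilot table in XI.2, so it is a category in use at the site.

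**Step 2. Which list does the protocol's arithmetic follow?** VI.14 has 24,000 patients a year for two years, of whom the selected lines cover 80%: 24,000 × 2 × 0.80 = 38,400. It states 3,840 per line, and 38,400 / 10 = 3,840. Nine lines would give 4,267 and six would give 6,400. VI.14 therefore uses ten lines, as in VI.13.

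**Step 3. Reproduce the protocol's power inputs.** XI.2 uses 40% v 28%, 500 per arm, and a logit SD of 0.20 between lines.

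- With no between-line variation, a two-sided 5% comparison of 40% and 28% with 500 per arm gives 98.0%. The protocol states 98%.
- Intra-cluster correlation: 0.20² × 0.40 × 0.60 = 0.0096, and 0.0096 / 1.0096 = 0.0095. The protocol states about 1%.

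**Step 4. Power by number of lines, L.** Assume 1,000 pairs spread evenly, so m = 1,000 / L pairs per line, with half the lines in each arm.

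- Variance of one line's observed rate: v(p) = [0.20 × p(1 − p)]² + p(1 − p)/m
- Standard error of the difference: SE = √{2[v(0.40) + v(0.28)] / L}
- Standardised difference: δ = 0.12 / SE
- Power from the noncentral t with L − 2 degrees of freedom, or from the normal as Φ(δ − 1.96)

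For L = 10, m = 100:

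- v(0.40) = 0.048² + 0.24/100 = 0.004704
- v(0.28) = 0.04032² + 0.2016/100 = 0.003642
- SE = √(2 × 0.008346 / 10) = 0.04086, so δ = 2.94

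| Lines | m | δ | t critical value | Power, t | Power, normal |
|---|---|---|---|---|---|
| 10 | 100 | 2.94 | 2.31 | 73% | 84% |
| 9 | 111 | 2.86 | 2.36 | 69% | 82% |
| 8 | 125 | 2.78 | 2.45 | 64% | 79% |
| 6 | 167 | 2.56 | 2.78 | 50% | 73% |

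Nine lines cannot split evenly. A 5:4 split gives 68% or 69% on the t reference, depending on which arm has five.

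**The case against.** A reader might infer that hernia and plastic would go unrecruited. The documents do not support this. VII.D.2 answers a privacy question about record access; it does not define eligibility or clusters. Recruitment is also described in VI.15 and VII.D.29, where "Any patient meeting inclusion criteria that the surgeon obtains surgical consent for could be captured" and the EPIC list is filtered by type of surgery, surgeon and date, with no line names. Hernia may sit inside general abdominal, and breast inside general. Only plastic lacks a counterpart on any reading. This objection stands: it is not certain that any line would recruit nobody.

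A reader might also infer that breast or cardiac patients would be enrolled without an arm. VI.13 excludes procedures outside its list, and a patient with no allocated line has no kit type. On the text, the likely result is records viewed for patients who are then excluded. What remains is that the protocol does not say whether those patients belong to a named line.

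On power, the gap between the stated 85% and 73% at ten lines is not caused by the list. It comes from using a t rather than a normal reference. Only the fall from ten lines to fewer belongs to this point, and the six-line row rests on the count in XI.2, not on VII.D.2. Strictly, up to ten is also compatible with six.

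Finally, the planned primary test is an unadjusted chi-squared test, not a cluster-level one. In a simulation with the protocol's inputs it rejected in 94% of trials with ten lines and 92% with six. Under no effect, however, it rejected in 15% and 22% of trials instead of 5%, so those figures cannot be used to support the power claim.

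**Conclusion.** The inconsistency is real: ten lines in VI.13, nine differently named categories in VII.D.2, and both six and up to ten in XI.2. It bears on the conduct of the trial because line membership decides the arm, and the documents contain no mapping from procedure or surgeon to line.

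The stated 85% is roughly reached only with ten lines and a normal reference (84%). With the six lines named in the primary analysis, a cluster-level comparison has about 50% power on a t reference with 4 degrees of freedom, or 73% on a normal reference. These figures assume an even spread of pairs, one outcome per pair, and the protocol's rates and logit SD; uneven line sizes would change them. The documents do not establish that any line is lost, so the eight- and nine-line rows show sensitivity only and are not a forecast.

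**What to change.** Use one list of randomised lines, identical in VI.13, VII.D.2 and XI.2, and give its length wherever a count appears. Before randomisation, add a table that maps each EPIC procedure or surgeon to exactly one line, and state where hernia, breast and cardiac cases belong or that they are excluded. Use the same definition for specialty in the SAP. Restate the power for that number of lines, naming the test and its reference distribution.

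The cost is harmonised text, one mapping table and a rerun of the power calculation. The power figure is likely to be less favourable than 85%. The mapping needs to be fixed before allocation, since assigning procedures to lines once the arms are known would be open to bias.

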- Other - The attached poster which summarizes elements of the study consent will be made available as a visual aide/reminder for both the surgical team and the patients.
 - Consent Document

- VII.D.16** ***Are you requesting a waiver of documentation of consent (either no subject signature or no written document)?***
Yes

- VII.D.17** ***Choose one of the following to indicate why you are requesting that the IRB waive the requirement to obtain a subject signature as documentation of consent:***
- A.** The research presents no more than minimal risk (minimal risk means the probability and magnitude of harm or discomfort anticipated in the research are not greater in and of themselves than those ordinarily encountered in daily life or during the performance of routine physical or psychological examinations or tests)

AND

The study involves no procedures for which consent is normally required outside of a research context. *(This type of waiver is often permitted for a minimal risk mail-out survey that includes a cover letter with all elements of consent, and returning the survey indicates consent. You cannot request this waiver if the study also involves the use of any protected health information (PHI).)*

- VII.D.18** ***Explain why this meets the chosen criteria in A. or B. above:***
This applies only to the clinician subjects, and, this is minimal risk. We are not collecting provider identifiers. All bacteria collected from providers will receive a unique barcode that will not be linked to the specific provider, only to the type of provider (anesthesia attending or anesthesia assistant).

- VII.D.19** ***Before the subject gives consent to participate are there any screening questions that you need to directly ask the potential subject to determine eligibility for the study?***
Yes

- VII.D.20** ***List any screening questions you will directly ask the potential subject to determine eligibility.***
Are you allergic to iodine, shellfish, or chlorhexidine? If the answer is yes, they will not be enrolled

- VII.D.21** ***Will you keep a screening log or other record that would include information on people who do not enroll in the study?***
Yes

- VII.D.22** ***Describe the information being collected and the purpose for keeping this information.***
For each service line, we will collect age and sex for those patients so that we can assess for biases, such as selection bias.
We will also track patients who did not send the kits in (via EPIC reports). These patients will not undergo surveillance because they will not have

completed the required screening component. If three calls are made and they do not use the kits, they will be considered lost to f/u. This will be important information when results are reported.

VII.D.23 *Will this information be shared with anyone outside the UI research team members?*
No

VII.D.25 *After the subject agrees to participate (signs consent), are there any screening procedures, tests, or studies that need to be done to determine if the subject is eligible to continue participating?*
Yes

VII.D.26 *List and describe screening*
As described in VII.D.22, the patient must use and return the preoperative swab kits. Three reminders will be provided. If they do not complete the initial screening process, they will be considered lost to f/u. Information required to meet inclusion criteria will be self evident (age which is in the chart, surgical service line which is already known...they are in the randomized line, and need for general/regional anesthesia (this is decided by the procedure).

VII.D.27 *Discuss how much time a potential subject will have to agree to consider participation and whether or not they will be able to discuss the study with family/friends before deciding on participation.*
The patient will be seen in clinic, PAT, or on the floor/ICU as part of their visit. The initial time to decide will be limited by the study visit, as a preoperative order must be placed. However, they will be able to decline at any point down the road as previously described, including simply deciding not to use and return the ordered kit.

VII.D.28 *How long after the subject agrees to participate do study procedures begin?*
Our goal is to focus on a 10-day window prior to surgery so that the kit can be shipped (two days), received (two days), processed (up to 2 days), and in the treatment group, treated for 2-4 days.

VII.D.29 *Provide a description of the enrollment and consent process for adult subjects*

- *Describe each study population separately including control population*
- *Include when recruitment and consent materials are used*
- *Use 3rd person active voice "The Principal Investigator will identify subjects. For example, the principal investigator will identify potential subjects, the study coordinator will discuss the study with subjects over the telephone and schedule the first study visit, etc..."*
- *Describe the steps that will be taken by the research team to minimize the possibility of coercion or undue influence during the consent process*

We will be attempting to capture all patients that meet inclusion criteria which could include patients seen and consented in the clinic, seen and consented on the hospital floor, intensive care units (inpatient surgery), or pre-anesthesia testing (PAT). Any patient meeting inclusion criteria that the surgeon obtains surgical consent for could be captured and tracked by the preoperative order.

Preoperative signed and held orders for preoperative swab kits will populate a list in EPIC for the PI ([name]). This list will be filtered by type of surgery, surgeon, and date of surgery within 10 days. Members of the research team will send out the kits after approval from the PI. Either treatment or control kits will be sent based on the service line, which will be linked by the kit number, and this will determine delivery of usual care or the treatment bundle on the day of surgery.

Before a kit is sent to the patient, a new signed and held order will be placed and associated with the kit number (specific to the kit sent to the patient) which will update the EPIC list with the kit number. The kits sent by the patient to RDB will be accomplished by a prepaid mailer. Patients will use and return the kits to RDB.

RDB will receive and process the kits. RDB will track the returned kit numbers and provide a list to [name]. [name] will complete the signed and held orders for patients in the Clarity report that returned kits for processing.

The completed POC will again update the Clarity report. The research assistants will work the list to select 2 patients with completed POC orders, treatment and control, for OR PathTrac Observation each day.

The assistants will confirm 1st patient consent. Once confirmed, an OR PathTrac Kit will be ordered in EPIC, a consent confirmed box checked in the RDB microEMR, and the preoperative swab and OR PathTrac kit numbers entered along with baseline patient demographic information.

Informed, written consent will be obtained from the second patient and the process repeated. If the second patient does not provide consent for their samples, the pair will be excluded and recruitment continued to reach a total of 1,000 complete pairs. Our prior experience at multiple centers and recent experience at the University of Iowa strongly suggests that patient refusal to provide written, signed consent for intraoperative samples will be a rare event. The assistant will then follow the 1st patient to the recovery area for sampling as previously described.

Providers: We will send out an email to all providers (anesthesia attending physicians, anesthesia residents, and circulating nurse anesthetists) that describes the study. A sample email has been attached which was based on that used for the OR PathTrac study. Providers will be given the opportunity to opt out. If they email a statement that they would not like to be involved, they will not be approached on the study day. If they do not provide a written response, they will be approached, but they can still opt out. This will be explained. If they opt out at that time, their name will be added to the list of providers who are not to be approached. This is to avoid coercion. When providers are approached in the case that they have not opted out, they will simply be reminded of the study, the purpose of the study, and they will be asked to dip their hand in a bag of sterile, balanced electrolyte solution. They will also be asked to use provided hand hygiene and catheter disinfection systems (treatment bundle). The hand hygiene solution was previously used in the OR PathTrac study, and providers are familiar with this solution. There were no issues previously. If they opt out, other providers will be sampled in the case that they do not opt out so as to maximize the efforts put forth by patient participation prior to the OR date and provider assignment to the patient's surgery.

VII.D.37

Does the study include any form of deception (e.g., providing participants with false information, misleading information, or withholding information about certain study procedures)?

Examples:

- *Procedure includes a cover story that provides a plausible but inaccurate account of the purposes of the research.*
- *Participants will be provided with false information regarding the particular behaviors of interest in the research.*

- *Procedures include a confederate pretending to be another participant in the study.*
- *Participants will be told that the research includes completion of a particular task, when in fact, that task will not be administered.*
- *Study is designed to introduce a new procedure (or task) that participants are not initially told about.*
- *If yes, a waiver of informed consent must be requested under question IV.3.*

No

VII.E. Project Description (E)

VII.E.1 *Will subjects be randomized?*

Yes

VII.E.1.a *Will any subjects be blinded to which study arm they have been assigned?*

Yes

VII.E.1.b *Does the protocol permit telling subjects their treatment assignment at the end of the entire study?*

No

VII.E.1.d *Justify why subjects cannot be told what study arm they have been assigned. You will need to disclose to subjects in the consent document that they cannot receive this information.*

This is a quality improvement project protected by quality assurance.

VII.E.2 *Describe randomization scheme/assignment including ratio such as 1:1, 2:1 etc.*

The service lines have been previously described. These lines will be randomized 1:1 to treatment (bundle) and usual care. This randomization will be computer generated by RDB software.

VII.E.3 *Will any questionnaires, surveys, or written assessments be used to obtain data directly from subjects in this study?*

No

VII.E.5 *Does this project involve creating any audiotapes, videotapes, or photographs?*

No

VII.E.6 *Provide a detailed description in sequential order of the study procedures following the consent process - DO NOT cut and paste from the Consent Document.*

Describe study populations separately if they will be participating in different procedures - include CONTROL population if applicable.

DESCRIBE:

- *What subjects will be asked to do/what happens in the study (in sequential order)*
- *The time period over which procedures will occur*
- *The time commitment for the subject for individual visits/procedures*
- *Long-term followup and how it occurs*

Preoperative swab kit orders will track informed, written consent and will populate a list in EPIC for the PI ([name]) that will be sorted by type of surgery and filtered (at the top of the list) by patients with orders for the kit that are actually booked for surgery within 10 days of the current date. That list will be used by [name] to send kits to patients for preoperative swabbing and if in the treatment group, decolonization with Povidone iodine. Before sending, a new signed and held POC preoperative swab kit order will be placed and associated with the kit number. The kits will be sent by the research team to the patient along with a prepaid mailer. The kit will include 3 swabs (nasal, axillary, and groin), preprinted instructions for use, and an insert briefly summarizing the study for a reminder (see attached documents). The patient will follow the kit instructions and send the kit to RDB for processing.

RDB will process the samples and enter the results into the software platform. RDB will send a list of kit numbers received to [name]. [name] will complete the signed and held order in EPIC for those received. This will create an ICON indicating complete. The complete ICON will guide OR PathTrac Surveillance, where a treatment and control patient are selected each day, as geographically dispersed as possible in the OR.

Patients in treatment lines with completed orders who are selected for surveillance will receive the treatment bundle (see below). Patients in usual care lines with completed orders who are selected for surveillance will receive usual care. All second patients in the observational pairs described below will receive usual care. Only the first patient in a treatment pair will receive the bundle (The goal is to examine the impact of an evidence-based bundle in preventing spread of bacteria from one patient to another).

For surveillance in the OR for both treatment and control patients selected for observation, the observational unit will be a case pair. The first patient will have been previously consented. This will be confirmed by the research assistants. An OR PathTrac Kit will be ordered by [name] or another physician research team member once consent is confirmed. The OR PathTrac and preoperative swab kit numbers will be entered into the RDB microEMR along with patient demographic information. Source documents will include a screen shot of the microEMR page with kit numbers and demographics and the kit insert. The OR surveillance as directed by the OR PathTrac kit will be conducted. The kits will be transported to RDB by the research team for processing. RDB will enter the results into the software platform.

The second patient will be approached for informed, written consent by the research team. This document is distinct from the first patient consent, as the second patient will not receive Povidone iodine, will not be asked to use the preoperative swab kit, and will not undergo postoperative surveillance. Only the OR PathTrac kit surveillance (while they are in the OR) will be conducted for the second patient. Once written consent is obtained, an OR PathTrac Kit will be ordered by [name] or another physician research team member, the kit number associated with the first patient's preoperative swab kit and OR PathTrac kit numbers in the microEMR, and the demographic information entered into the microEMR as well. Source documents will include a screen shot of the microEMR page with kit numbers and demographics and the kit insert. The OR surveillance as directed by the OR PathTrac kit will be conducted. Kits will be transferred to RDB by the research team. RDB will process the kits and enter the results into the software platform. OR PathTrac kit orders electronically confirm obtained written consent.

The first patient will be followed to the recovery period. A ward environment surveillance (WES) kit will be used for surveillance. The kit will be associated to the above information in the microEMR as previously described. Ward (this is the recovery area, could be the intensive care unit, post anesthesia care unit, second stage recovery, a hospital floor, etc) surveillance will be conducted as directed by the kit. Kits will be

transferred to RDB by the research team. RDB will process the kits and enter the results into the software platform.

The treatment bundle will continue with the first patient for up to 48 hours into their recovery period. Usual care patients, and all second patients in a pair, will continue with usual care.

Treatment and control patients will be followed for up to 90 postoperative days to identify the occurrence of one or more healthcare-associated infections according to National Healthcare Safety Network (NHSN) definitions and will be called at the 90 day mark (up to 3 attempts will be made) to determine if they developed an infection. A research assistant will review the patient's electronic medical record via EPIC for bacteriology results for urine, sputum, wound, sterile sites and blood. If a positive culture is identified, the RA will provide the UIHC Clinical Lab with an accession number so that the isolate can be saved. Samples will be sent to RDB for analysis in order to determine if the organism was clonally-related to an organism isolated from one or more reservoirs during the pre/peri/post-operative period. At no point will personal ID information be attached to isolate(s).

All microbiological data will be entered into the RDB software platform. The platform will identify transmission events. This information will be graphically displayed, continually updated, and will bring genomic analysis to the bedside by providing a mechanism for the research team to continually optimize treatment bundle delivery.

The above process is summarized in the diagrams attached in the misc. documents. These diagrams, along with bullet points of the study in poster format, will be placed on the wall of physician offices where consent will be taking place to remind providers of the study and to serve as a visual aide for the patient during the consent process. The information on the posters will simply state the purpose of the study and participation requirements as outlined in the consent. Please see the poster attached in miscellaneous.

Procedures:

Preoperative, Intraoperative, and Postoperative Patient Culture Procedures:

This will involve use of a sterile ESwab to obtain nasal, axillary, and inguinal swabs. Nasal: the swab is to be inserted into each nares no more than 3/4 of an inch and rotated 360 degrees 10 times. Axillary: the swab will be applied to the middle of the armpit, pressed firmly against the skin, and rotated 10 times. Inguinal: the swab will be applied to the inguinal crease, pressed firmly against the skin, and rotated 10 times. After collection, each swab will be inserted into the collection medium (Aimes transport medium), the applicator stick snapped off as directed, and the cap placed on the tube to seal the contents.

Treatment Bundle:

Decolonization: Each patient in the treatment group will receive Povidone iodine treatment for their nose and potentially their surgical site on the day of surgery in the Day of Surgery Admissions(DOSA) area. The surgical team will approve and guide the application of the povidone iodine to the likely surgical incision site(s) or it will not be placed. The application of the povidone iodine to the inside of the nose will be guided by a member of the research team. 2% Chlorhexidine body Wipes are currently used in UIHC Day of Surgery Admission (DOSA) to help disinfect patient skin before surgery

and we will make sure that treatment patients are properly administered these wipes and educated on their use.

Vascular care: Each patient in the treatment group will receive the Ultrapore zero (BBraun Medical) closed, disinfectable stopcock set and the DOCit and HubScrub disinfection system (Saxa Medical). The DOCit is a cap that providers in the OR will insert syringes into to keep them free of environmental contamination, organized, and sterile given the 62% isopropyl alcohol in each cap. This is a FDA approved device that is on the market. It has been shown to reduce infections with a number needed to treat of 16. The HubScrub is a cap with the same disinfectant that providers will use to scrub the injection ports, or stopcock sets. This cap contains 62% alcohol and brushes for mechanical disruption of biofilms. The cap disinfects the port in 10 seconds, maintains disinfection for >72 hours when covered, and only needs to be turned 2 times to disrupt any biofilm. It is also evidence based and proven to reduce infections. It is also FDA approved and on the market. The DOCit and HubScrub systems will be provided in the preoperative area, affixed to the IV pole for easy access by the anesthesia provider in the OR, and transported with the patient to the recovery unit.

Hand Hygiene: The Saxa system also contains a single-handed hand hygiene device that allows the provider to disinfect their hands at every opportunity. It is affixed to the IV pole and will be used preoperatively, intraoperatively, and postoperatively.

Environmental cleaning: Surveillance will map ORs affected by residual contamination with hyper transmissible, resistant, and virulent organisms. This information will be communicated to the environmental cleaning service in the OR electronically, automatically updated each day, in order to guide improved routine and terminal cleaning for affected ORs. Improved routine cleaning will involve use of the conventional quaternary ammonium compound with a microfiber cloth followed by a surface disinfection wipe. Improved terminal cleaning will involve robotic cleaning using UV robots (using UV light in the OR for under an hour) at night/morning if not being used, or will involve increased duration of application of the previously described cleaning procedure.

